### Sample transfer

We may send anonymized data collected as part of the study (e.g. questionnaire responses, genetics, interview recording, biological samples) outside the European Economic Area (EEA). The information will only be used by organisation and researchers to conduct research in accordance with the UK Policy Framework for Health and Social Care Research.

## 9 Financial Information and Insurance

The study is funded by the Medical Research Council.

No-fault compensation insurance cover for any non-negligent harm will be provided by University College London.

## 10 Publications Policy

All individuals who have made substantial intellectual, scientific and practical contributions to the study and the manuscript should, where possible, be credited as authors; all individuals credited as authors should deserve that designation. It is the responsibility of the Chief Investigator and co-PI and, ultimately, the Sponsors to ensure that these principles are upheld. The status of manuscripts in preparation will be reviewed by the chief Investigator and sponsor if requires. In all cases where journal policies permit, all investigators who contribute patients to the study will be acknowledged.

The results of the study will be reported and disseminated as follows:

- Peer reviewed scientific journals
- Internal report, plus possible article on Institute web pages (publicly accessible)
- Conference presentations
- Written feedback to patient support groups.

## Appendix B: Demographic updates, Study Impact Questionnaire & Covid Impact Questionnaire

### Demographic Updates

Thank you for completing the IMAGINE Questionnaires. We'd like to find out if anything has changed since you last completed some questionnaires:

1. **What is your age:**
2. **Your partner's age (if applicable):**
3. **Your child's age:**
4. **Ethnicity:**

- White British
- White Irish
- Any other white background
- Black or Black British Caribbean

- Black or Black British African
- Any other Black background
- Mixed White and Black Caribbean
- Mixed White and Black African
- Mixed White and Asian
- Any other mixed background
- Indian
- Pakistani
- Bangladeshi
- Chinese
- Any other Asian background
- Any other ethnic group
- Unknown

**5. What is the name of your child's school?**

**6. What is your current postcode?**

**7. What is your highest education level?**

- Left school before exams
- O-levels or GCSEs
- A-levels or Highers
- University degree
- Higher or postgraduate degree
- Vocational training
- Not known

**8. What is your current employment status/ situation?**

- Full time paid employment
- Part time paid employment
- Currently unemployed
- Full time training or education
- Part time training or education
- Voluntary work
- Other (please specify)

**9. What is your yearly household income?** "Household income" means the money brought in by you and/or your spouse and/or another adult you live with, with whom you share finances. Don't count the income from anybody whose finances are independent of yours.

- Less than £16,000 a year (£310 a week)
- £16,000-£29,999 a year (£310 - £579 a week)
- £30,000-£59,999 a year (£580 - £1149 a week)
- £60,000-89,999 a year (£1500 - £1729 a week)
- £90,000-119,999 a year (£1730 - £2299 a week)
- More than £120,000 a year (£2300 a week)
- Prefer not to say

**10. In the past year, have you or your child had help or advice on his emotions, concentration or behaviour from any of the following?**

- Someone in your family or a close friend
- Books or magazines
- The internet
- Telephone help-line
- Self-help group

**11. In the past year, have any of the following professionals been involved in the care of your child?**

- A teacher (such as a class teacher, head of year, special educational needs coordinator)
- Special educational needs staff in school (e.g. learning support assistant)
- Educational psychologist
- Your GP, family doctor, health visitor
- Someone specializing in young people's general health (such as a paediatrician, school nurse, school doctor, or speech therapist)
- Someone specializing in mental health (such as a counsellor, psychologist or psychiatrist)
- Someone from social services (such as a social worker or family support worker)
- Someone else

**12. A. Does your child have a diagnosis of the following: (Please tick all that apply)**

- Autism Spectrum Disorder
- Attention Deficit Hyperactivity Disorder
- Conduct Disorder/Oppositional Defiant Disorder
- Anxiety Disorder
  - If yes: Social Phobia, Generalized Anxiety Disorder
- Mood disorder
- Attachment Disorder
- Tourette's Disorder/Tic disorder
- Seizures/Epilepsy
- Specific Learning Disability
- Intellectual Disability
- Developmental Delay
- Other:

**B. We'd like to know whether your child has received any new diagnoses since you completed the Imagine-1 DAWBA questionnaire. Were any of these new diagnoses?**

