#### **5. Demographic updates (10 min)**

This questionnaire will allow us to understand changes in circumstances over the 5 year period. The questionnaire will include questions on changes in the child's address, mental health diagnoses, schooling and support received (Appendix B).

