**13. Is there another child living at home?**

- Yes
- No

**If yes, does your child's sibling (half, full or adopted) have any of the following diagnoses: Please tick all that apply**

- Autism Spectrum Disorder
- Attention Deficit Hyperactivity Disorder
- Conduct Disorder/Oppositional Defiant Disorder
- Anxiety Disorder
  - If yes: Social Phobia, Generalized Anxiety Disorder

- Mood disorder
- Attachment Disorder
- Tourette's Disorder/Tic disorder
- Seizures/Epilepsy
- Specific Learning Disability
- Intellectual Disability
- Developmental Delay
- Other:

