#### **Behavioural impact**

**Did you show your summary report to anyone?** (Please tick all that apply)

- I did not show anyone the report
- Other members of my family
- A teacher (such as a class teacher, head of year, special educational needs coordinator)
- Special educational needs staff in school (e.g. learning support assistant)
- Educational psychologist
- Your GP, family doctor, health visitor
- Someone specializing in young people's general health (such as a paediatrician, school nurse, school doctor, or speech therapist)
- Someone specializing in mental health (such as a counsellor, psychologist or psychiatrist)
- Someone from social services (such as a social worker or family support worker)
- Someone else – please specify:

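### In Appendix B, Q10, Q11 and the Q13 sibling list have no 'none' option, so a blank cannot separate 'none' from 'not answered'

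*Protocol*

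**What the plan says.** Section 5.5 (annual follow-up, item 5) gives the Demographic Updates form the task of recording changes over the five years in, among other things, "mental health diagnoses, schooling and support received". Section 4.1 asks whether the support families received over that period influenced the young person's adjustment or risk of disorder.

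The items are printed in Appendix B:

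- **Q10** asks "have you or your child had help or advice on his emotions, concentration or behaviour from any of the following" and lists five sources, from family or friends to a self-help group. It has no 'other' and no 'none'.
- **Q11** asks "In the past year, have any of the following professionals been involved in the care of your child" and lists eight kinds of professional, the last a catch-all. It has no 'none'.
- **Q12A** asks "Does your child have a diagnosis of the following: (Please tick all that apply" and lists twelve main conditions, including intellectual disability and developmental delay. It has no 'none'. **Q12B** then asks "Were any of these new diagnoses" and prints no response options.
- **Q13** opens with a Yes/No question, "Is there another child living at home", and then asks "does your child's sibling (half, full or adopted) have any of the following diagnoses: Please tick all that apply". The list has no 'none'.

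Other items in the appendix do provide for a negative or a non-answer. The income question (Q9) allows the respondent to decline, the education question (Q7) allows 'not known', and the question on who saw the summary report offers "I did not show anyone the report".

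**The concern.** A list with only positive options uses a blank for two different things: the honest answer 'none' and no answer at all. That information is lost when the data are captured. A later missing-data method can only work on values known to be missing, so it cannot restore the distinction.

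What is at stake is the comparison between supported and unsupported families that section 4.1 sets up, and the yearly tracking of support described in section 5.5. If blanks were read as 'none', supported families who skipped would be counted as unsupported, and an apparent loss of support between waves could simply be a skipped item. Skipping may also be related to family burden, in which case the error would not be random.

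**Working it through.** The plan gives no figure to reproduce, so the check is a reading of each item followed by an illustration of size.

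**Step 1: what a blank can mean, item by item.**

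| Item | 'None' option printed? | What a blank list can mean |
|---|---|---|
| Q10 | No | No help, or skipped |
| Q11 | No | No professional involved, or skipped |
| Q13 list, after 'Yes' | No | Sibling without a diagnosis, or skipped |
| Q12A | No | Almost certainly skipped |
| Q12B | No options printed | No new diagnosis, or skipped |

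The Q13 gate asks only whether another child lives at home. It separates families with no sibling at home from the rest, but does not separate an unaffected sibling from an unanswered list.

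Q12A differs because of eligibility. Section 4.4 requires an intellectual disability or developmental delay diagnosis for every IMAGINE-1 proband, and the synopsis requires intellectual disability for self-referrals. Both conditions are on the Q12A list, so an eligible family that answers should tick at least one box.

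**Step 2: possible size for support, if blanks are read as 'none'.**

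Inputs, none of which the documents give:

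- *s*, the share of families skipping the list: 5-10% (assumed)
- *p*, the true share with some support: 50% or 70% (assumed)
- Skipping is independent of support status (assumed)

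The apparent no-support group holds all truly unsupported families (1 − *p*) plus supported families who skipped (*s* × *p*). The supported share of that group is

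*c* = *s p* / [(1 − *p*) + *s p*].

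- *p* = 50%, *s* = 5%: 0.025 / 0.525 = 4.8%
- *p* = 50%, *s* = 10%: 0.050 / 0.550 = 9.1%
- *p* = 70%, *s* = 5%: 0.035 / 0.335 = 10.4%
- *p* = 70%, *s* = 10%: 0.070 / 0.370 = 18.9%

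The share rises with true support. At *p* = 90% (assumed) it would be 0.045 / 0.145 = 31% to 0.090 / 0.190 = 47%. This matters for Q11 in particular, whose list includes teachers and GPs.

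**Step 3: effect on a comparison.** If supported and unsupported families differ by *D* on some outcome, the blank group's mean is a mixture of the two, and the observed difference is (1 − *c*) × *D*. Under the four main settings above, a difference would shrink by about 5% to 19%. If skipping depends on support or on the outcome, the bias could be larger or smaller.

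**The case against.** - **The appendix gives question wording, not the REDCap build.** Q10 and Q11 carry no tick-all instruction, and Q12B, Q14 and Q15 print no response field. If each line is built as a separate Yes/No, the ambiguity disappears. This stands, and it makes the point conditional on the form being used as printed. Required fields alone would not be enough, because without a 'none' option a family with no support would have to tick something untrue. Section 5.5 also allows posted paper forms, where nothing can be enforced, although post and telephone together serve fewer than 1 in 10 participants.
- **No specified analysis uses these items.** New psychiatric disorders in section 6.1 come from the SDQ, ABAS-3 and the five-year DAWBA, and the listed moderators do not include Q10, Q11 or sibling diagnoses. This stands and is the main reason the point is minor. Sections 4.1 and 5.5 still state an intention to study support.
- **Service use is also captured by record linkage.** This holds only in part. Families may opt out of linkage (section 5.2), and friends, books, the internet, help-lines and self-help groups do not appear in hospital or school records.
- **Missing covariates belong in the SAP.** Agreed. Section 6.1 describes FIML for problem behaviour and adaptive functioning, and its silence on these items is not a fault. The point concerns the form, which has to let missing values be recognised before any method can be applied.

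**Conclusion.** The point holds for Q10, Q11 and the Q13 sibling list as printed: 'none' and 'not answered' give the same blank. If blanks are read as 'none', supported families would make up about 5-9% of the apparent no-support group at 50% true support and 10-19% at 70%. These figures rest on an assumed 5-10% skip rate, assumed support rates and skipping unrelated to status. The point is minor, and the primary SDQ trajectory is unaffected.

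Two stronger readings are tempting but not supported:

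- A reader might infer that the study records a skipped list as no support or no diagnosis. The protocol states no coding rule for blanks and does not say whether fields are mandatory.
- A reader might multiply the 57% of IMAGINE-1 participants with a psychiatric diagnosis by a 5-10% skip rate and conclude that roughly 3-6% of the cohort (0.57 × 0.05 to 0.57 × 0.10) would appear free of diagnoses. The 57% is not the share who would tick something in Q12A. By eligibility that share should be close to 100%, so an all-blank Q12A shows itself as a skip.

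**What to change.** - **Form.** Add 'None of these' and 'Don't know / prefer not to say' to Q10, Q11 and the Q13 list, and optionally to Q12A. Add Yes/No to Q12B. Once those options exist, require one response per list in REDCap.
- **Future waves.** Code an all-blank list as missing.
- **Waves already collected.** Code an all-blank Q12A as missing. Keep an all-blank Q10, Q11 or Q13 list as indeterminate, and report a sensitivity analysis that treats it once as 'none' and once as missing. Coding all of these as missing would delete every genuine 'none': everyone left in Q10 would have had help, and every sibling left in Q13 would have a diagnosis. If the live REDCap form already has a negative option or line-by-line Yes/No, state this and use those codes.

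The cost is a minor form amendment, a validation rule and seconds of respondent time. The item format also changes between waves, so the wave of the change should be recorded and a shift in reported support at that point read with care.

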**13. Is there another child living at home?**

- Yes
- No

**If yes, does your child's sibling (half, full or adopted) have any of the following diagnoses: Please tick all that apply**

- Autism Spectrum Disorder
- Attention Deficit Hyperactivity Disorder
- Conduct Disorder/Oppositional Defiant Disorder
- Anxiety Disorder
  - If yes: Social Phobia, Generalized Anxiety Disorder

- Mood disorder
- Attachment Disorder
- Tourette's Disorder/Tic disorder
- Seizures/Epilepsy
- Specific Learning Disability
- Intellectual Disability
- Developmental Delay
- Other:

**14. At present, roughly what sort of age level is he/she at in her school work and ability to reason things out?**

**15. At present, roughly what sort of age level is he/she at in her use and understanding of language?**

### Study Impact and Feedback

As part of IMAGINE-ID online study we sent you a report summarising your child's strengths and difficulties. We'd like to ask you a few questions about the report, to find out whether it had an impact and find out how to improve it. We'd also like to ask you a few questions about your experiences of taking part in the study in general.

#### **Behavioural impact**

**Did you show your summary report to anyone?** (Please tick all that apply)

- I did not show anyone the report
- Other members of my family
- A teacher (such as a class teacher, head of year, special educational needs coordinator)
- Special educational needs staff in school (e.g. learning support assistant)
- Educational psychologist
- Your GP, family doctor, health visitor
- Someone specializing in young people's general health (such as a paediatrician, school nurse, school doctor, or speech therapist)
- Someone specializing in mental health (such as a counsellor, psychologist or psychiatrist)
- Someone from social services (such as a social worker or family support worker)
- Someone else – please specify:

#### **Clinical impact**

Receiving the IMAGINE-ID Summary report led to... Please tick the appropriate boxes	Yes	No	Not applicable
improvements in my child's treatment and/or care plan			
improvements in my child's access to physical health care			
improvements in my child's access to mental health care			
improvements in my child's access to behavioural support			
improvements in our communication with medical professionals			
getting in touch with a patient support group			
a referral for autism spectrum disorder assessment			
a referral for attention deficit hyperactivity disorder			

assessment			
a referral for any other assessment or appointment			

Please use the space below to add any further comments:

### **Social impact**

**Did you use the report as supporting evidence to access services?** (Please tick all that apply)

- No  
 Yes

If yes:

- Disability Benefits  
 Special Educational Needs Support  
 Educational Health Care Plan  
 Other (please specify):

### **Psychological impact**

For each statement please circle the number from 1 to 5 that best describes how you feel

Did the summary report help you to understand your child's strengths and difficulties compared to other children?

Not helpful      1      2      3      4      5      Very helpful

Did the summary report change the way you thought about your child's behaviour?

No change      1      2      3      4      5      Change

Did the summary report help/empower you to seek additional support for your child?

Not helpful      1      2      3      4      5      Very helpful

Did the summary report help you to feel more in control of your child's behaviour?

Not helpful      1      2      3      4      5      Very helpful

### **Attitudes towards feedback**

For each statement please circle the number from 1 to 5 that best describes how you feel

For me and my child, receiving the summary report was:

Not helpful      1      2      3      4      5      Very helpful

For me and my child, taking part in the Imagine study was:

Not helpful      1      2      3      4      5      Very helpful

**Feedback**

**Do you feel the report accurately represented your child's strengths and difficulties?**

- Yes  
 No  
 Don't know

Any further comments on the report:

**Is there anything we could do to improve the report?**

- Yes  
 No  
 Don't know

Any further comments on the report:

**Is there anything we could do to improve your experience of taking part in the Imagine study?**

- Yes  
 No  
 Don't know

Please use the space below to add any further comments on taking part in the study:

### The impact of the Coronavirus/ COVID-19 pandemic on your family

The Coronavirus/ COVID-19 pandemic has been difficult for many families. The following questions will help us understand what has happened in your family and how your child with a Rare Genetic Condition has coped during this crisis. There are no right or wrong answers.

**Interviewer –**

**Child's name –**

**Participant/relative's ID number –**

**Family questions (to be asked *once* if sibling and proband have the same family).**

- 1. During the Coronavirus/ COVID19 pandemic has anyone in your child's family been diagnosed with Coronavirus/ COVID-19? (check all that apply)**
  - a. Yes, member of household
  - b. Yes, non-household member
  - c. No

- 2. During the Coronavirus/ COVID19 pandemic have any of the following happened to your child's family members because of Coronavirus/ COVID-19: (check all that apply)**
- a. Fallen ill physically
  - b. Hospitalized
  - c. Put into self-quarantine with symptoms
  - d. Put into self-quarantine without symptoms (e.g., due to possible exposure)
  - e. Lost job
  - f. Reduced ability to earn money
  - g. Passed away
  - h. Does not apply
- 3. During the Coronavirus/ COVID-19 pandemic to what degree have changes related to the Coronavirus/COVID-19 crisis in your area created financial problems for your family?**
- a. Not at all
  - b. Slightly
  - c. Moderately
  - d. Very
  - e. Extremely
- 4. How stressful have you found life during the Coronavirus/ COVID-19 pandemic?**
- a. Not at all
  - b. Slightly
  - c. Moderately
  - d. Very
  - e. Extremely

Please explain \_\_\_\_

- 5. During the Coronavirus/ COVID19 pandemic has your child with a Rare Genetic Condition been exposed to someone likely to have Coronavirus/ COVID-19? (check all that apply)**
- a. Yes, someone with positive test
  - b. Yes, someone with medical diagnosis, but no test
  - c. Yes, someone with possible symptoms, but no diagnosis by doctor
  - d. No
- 6. During the Coronavirus/ COVID19 pandemic has your child with a Rare Genetic Condition been suspected to have Coronavirus/ COVID-19 infection?**
- a. Yes, has tested positive
  - b. Yes, medical diagnosis, but no test
  - c. Yes, has had some possible symptoms, but no diagnosis by doctor
  - d. No symptoms or signs
- 7. People who are at very high risk of severe illness coronavirus/ COVID-19 infection have been advised to shield. Shielding means minimising all interaction with others (even those one lives with). Has your child shielded during the Coronavirus/ COVID19 pandemic?**
- a. Yes, based on guidance from the NHS (my child received a letter/we were advised by our GP or hospital clinician)
  - b. Yes, because other family members were advised to shield
  - c. Yes, this was our personal decision
  - d. No

8. In general, during the Coronavirus/COVID19 pandemic how worried has your child been about being infected?
- Not at all
  - Slightly
  - Moderately
  - Very
  - Extremely
  - Cannot tell
9. In general, during the Coronavirus/COVID19 pandemic how worried has your child been about friends or family being infected?
- Not at all
  - Slightly
  - Moderately
  - Very
  - Extremely
  - Cannot tell
10. In general, during the Coronavirus/COVID19 pandemic how worried has your child been about their *physical health* being influenced by Coronavirus/ COVID-19?
- Not at all
  - Slightly
  - Moderately
  - Very
  - Extremely
  - Cannot tell
11. In general, during the Coronavirus/COVID19 pandemic has your child's behavior changed in a positive way due to Coronavirus/ COVID-19? (Check all that apply)
- No positive changes
  - Yes, more relaxed
  - Yes, happier
  - Yes, more confident
  - Other, please explain \_\_\_\_
12. In general, during the Coronavirus/COVID19 pandemic has your child's behavior changed in a negative way due to Coronavirus/ COVID-19? (Check all that apply).
- No negative changes
  - Yes, more irritable
  - Yes, more restless
  - Yes, less energetic
  - Other, please explain \_\_\_\_
13. In general, during the Coronavirus/COVID19 pandemic how worried has your child been about their *mental/ emotional health* being influenced by Coronavirus/COVID-19?
- Not at all
  - Slightly

- c. Moderately
- d. Very
- e. Extremely
- f. Cannot tell

**14. During the Coronavirus/ COVID-19 pandemic has your child's school building been closed?**

- a. Yes
- b. No
- c. **Child no longer in school (skip to question 17).**

**If no,**

- Have classes been in session? Y/N
- Did your child attend classes in-person? Y/N
- **Please explain**\_\_\_

